11.1.4.2 Secondary Safety Analysis

The definition of the other safety endpoints and the corresponding analyses will be detailed in the SAP.

11.1.4.3 Efficacy Variables

Efficacy will be assessed for the 12-month treatment period based on daily "ON" time without troublesome dyskinesia and daily "OFF" time as determined from "ON/OFF" home diary entries. Efficacy will be further explored using PDQ 39 (PD-QoL), EQ-5D-5L (general QoL), rating of PD (UPDRS), CGI for severity and improvement, and sleep assessment (PDSS).

The analysis of the efficacy data will focus on estimating the changes from baseline of the present study. The efficacy data will be summarized for both the total mITT Set and broken down by the treatment regimen (when applicable). Cohort 1 and Cohort 2 will be summarized separately (where applicable).

11.1.4.3.1 Definition of Efficacy Endpoints

The exploratory efficacy endpoints assessed for 12 months of treatment are:

- Change in daily "ON" time without troublesome dyskinesia (defined as the sum of "ON" time without dyskinesia and "ON" time with non-troublesome dyskinesia) from Baseline to the 12-month visit based on home "ON/OFF" diaries.
- Change in daily "OFF" time from Baseline to the 12-month visit, based on home "ON/OFF" diaries.
- Change in total daily dose of oral LD/DDI from Baseline to the 12-month visit.
- Proportion of responders at the 12-month visit based on daily "OFF" time recorded in home "ON/OFF" diaries. A responder is defined as a subject that experiences ≥50% reduction in "OFF" time from Baseline.
- Change in daily "ON" time with troublesome dyskinesia in a subset of subjects who had more than 1 hour of troublesome dyskinesia at Baseline, based on home "ON/OFF" diaries from Baseline to the 12-month visit.

- Change in PDQ-39 scores from Baseline to the 12-month visit.
- Change in EQ-5D-5L scores from Baseline to the 12-month visit.
- Change in UPDRS Part II (ADL) from Baseline to the 12-month visit.
- Change in CGI-Severity and CGI-Improvement from Baseline to the 12-month visit.
- Change in SGI-Improvement from Baseline to the 12-month visit.
- Change in PDSS total score from Baseline to the 12-month visit
- Change in UPDRS Part III (motor score) from Baseline to the 12-month visit.
- Change from baseline to month 12 in percentage of "OFF" time and percentage of 'Good' ON during the first 3 hours since the subject is awake after 06:00 (6 am)
- Change from baseline to month 12 in ND0612 total dose
- Proportion of patients who reduced ND0612 total dose at any time during the study

The first efficacy endpoint of the change from Baseline to Month 12 in daily "ON" time without troublesome dyskinesia will be based on subject diary data. This will be a within group analysis for each treatment regimen. Subjects will provide data on daily "ON" and "OFF" time for the 2 days prior to the following visits: Baseline (Cohort 2 only), Months 1, 3, 6, 9, and 12 and the Early termination visit (if applicable) and additionally at Months 18, 24, 30, and 36 of the extension period. Subjects in Cohort 1, will be excluded from this analysis.

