7.3 Efficacy Objectives

The following exploratory efficacy objectives will be assessed for a 12-month treatment period, separately for Cohort 1 (subjects who completed the treatment period of study ND0612H-006 within one month prior to enrolling to ND0612H 012) and Cohort 2 (ND0612 naïve subjects and subjects who completed the treatment period of any ND0612 study more than one month before screening of ND0612H-012):

- To assess the efficacy of continuous SC infusion of 2 dosing regimens of ND0612 on daily "ON" time without troublesome dyskinesia (defined as the sum of "ON" time without dyskinesia, and "ON" time with non-troublesome dyskinesia) based on home "ON/OFF" diaries
- To assess the efficacy of continuous SC infusion of 2 dosing regimens of ND0612 on daily "OFF" time based on home "ON/OFF" diaries
- To assess the efficacy of continuous SC infusion of 2 dosing regimens of ND0612 on total daily dose of oral LD/DDI
- To assess the effect of continuous SC infusion of 2 dosing regimens of ND0612 on the motor score and ADL scores of the UPDRS

- To assess the effect of continuous SC infusion of 2 dosing regimens of ND0612 on the proportion of subjects with an improvement of ≥50% in "OFF" time based on home "ON/OFF" diaries
- To assess the effect of continuous SC infusion of 2 dosing regimens of ND0612 on "ON" time with troublesome dyskinesia time (based on home "ON/OFF" diaries) in a subset of subjects who had more than 1 hour of troublesome dyskinesia at baseline.
- To assess the CGI (improvement and severity score assessed by investigator), Subject Global Impression (SGI-I: improvement score assessed by subjects), PDSS, the PDQ-39 and the EQ-5D-5L.

Efficacy analyses will be exploratory only; no formal hypothesis testing will be performed in this study.

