11.1.4.3.2 Methods of Analysis

All efficacy summaries and analyses will be produced for the mITT Set.

For the efficacy endpoints, continuous data will be summarized at each protocol scheduled time point, by treatment regimen, using summary statistics. Actual values and changes from Baseline will be presented. All categorical endpoints will be summarized at each protocol scheduled time point, by randomized treatment regimen, using frequency tabulations.

As the primary purpose of this study is to explore the 2 treatment regimens with regards to efficacy and safety and not to perform confirmatory analyses comparing the treatment

regimens, there will be no formal hypothesis testing performed and adjustments for multiplicity are not required.

The change from Baseline to Month 12 and to the other visits within each treatment regimen in daily "ON" time without troublesome dyskinesia will be estimated using a Mixed Model for Repeated Measures (MMRM) including response data from all scheduled post-baseline visits with no imputation for missing data. The changes from Baseline within each treatment regimen and the comparison between the Regimens will be estimated, separately for each scheduled study visit, from the same MMRM using contrasts. The treatment regimen (Regimen 1 or Regimen 3, when applicable), visit and the interaction between treatment regimen and visit (if applicable) will be included as fixed factors in the MMRM together with the baseline value as covariate. The analysis for the "ON/OFF" home diary, will be performed only for cohort 2. Changes from baseline will be summarized also the overall data. There will be no random effects. An unstructured covariance structure will be assumed, and the denominator degrees of freedom will be computed using the Kenward-Roger method.

The changes in "ON" time without troublesome dyskinesia will be estimated both as hours (normalized to 16 hours of awake time) and as a proportion out of awake time.

In general, all further efficacy endpoints will be summarized and analyzed using either a MMRM analysis, as described above, for continuous endpoints or descriptive statistics for categorical endpoints. Sensitivity analyses of efficacy data will be conducted by excluding the subjects who were randomized to receive Regimen 2. The definition of the endpoints and the statistical analyses will be detailed in the SAP.

Data collected in the extension period will be analyzed similarly as for the 12-month period.

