2.3. Exploratory Objectives

Exploratory efficacy objectives will be to assess the following:

- To assess the efficacy of continuous SC infusion of 2 dosing regimens of ND0612 on daily ON time without troublesome dyskinesia (“GOOD ON”) defined as the sum of "ON" time without dyskinesia and “ON” time with non-troublesome dyskinesia, based on home “ON/OFF“ diaries
- To assess the efficacy of continuous SC infusion of 2 dosing regimens of ND0612 on daily “OFF” time based on patient completed home “ON/OFF” diaries
- To assess the efficacy of continuous SC infusion of 2 dosing regimens of ND0612 on daily “ON“ time without any dyskinesia based on home “ON/OFF“ diaries
- To assess the effect of ND0612 on morning “OFF” time using subject-completed “ON/OFF” diary assessments of motor function.
- To assess the effect of continuous SC infusion of 2 dosing regimens of ND0612 on the motor and Activities of Daily Living (ADL) sub-scores of the Unified Parkinson’s Disease Rating Scale (UPDRS)
- To assess the effect of continuous SC infusion of 2 dosing regimens of ND0612 on the

ND0612H-012

Final 4.0

proportion of subjects with an improvement of $\geq 50\%$ in “OFF“ time based on home “ON/OFF“ diaries

- To assess the effect of continuous SC infusion of 2 dosing regimens of ND0612 on “ON” time with troublesome dyskinesia (based on “ON/OFF” home diaries) in a subset of subjects who had more than 1 hour of troublesome dyskinesia at baseline.
- To assess the Clinical Global Impression (CGI: improvement and severity score assessed by investigator), Subject Global Impression (SGI-I: improvement score assessed by subject), Parkinson’s Disease Sleep Scale (PDSS), the 39-Item PD Quality of Life [QoL] Questionnaire (PDQ-39) and the EQ-5D-5L QoL questionnaire.

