5. GENERAL ASPECTS FOR DATA ANALYSIS

5.1. General Methods

All data from all patients entered into the study will be included in patient data listings. The listings will be sorted by center, and patient number (and by visit, if applicable).

The data will be summarized using either descriptive statistics (number of non-missing observations, mean, median, SD, standard error of the mean (SEM), minimum and maximum) for continuous data or frequency counts and percentages for categorical data. For visit-specific data, the number of subjects with non-missing observations at the visit in question will be used as the denominator for percent calculations. Unknown, Not Done, Not Applicable and other classifications of missing data will not be considered.

The summaries will be broken down by treatment regimen (Regimen 1, Regimen 3) and by visit, as applicable. For demographic and other baseline characteristics and selected safety data, an overall column will be displayed in addition to the data broken down by the treatment regimen. Unscheduled or repeated assessments will not be included in summary tables but will be included in listings.

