- Baseline ON time without troublesome dyskinesia determined by “ON/OFF” diary (defined as the sum of ON time without dyskinesia and ON time with non-troublesome dyskinesia)
 - For derivation, see section 3.2.3

- Baseline “OFF” time as determined by “ON/OFF” diary (continuous)
 - For derivation of the “OFF” time, see section 3.2.3

- Baseline ON time without dyskinesia as determined by “ON/OFF” diary (continuous)
 - For derivation, see section 3.2.3.

- Baseline ON time with Troublesome dyskinesia as determined by “ON/OFF” diary (continuous)

- Total daily levodopa dose as IR levodopa equivalent dose (continuous); total administered daily levodopa dose (without conversion); total administered daily levodopa dose (without conversion) categorized as <400 mg or ≥400 mg.); daily levodopa dosing frequency (categorical); patients using COMT inhibitors, patients using carbidopa or benserazide as DDI. For conversion factors, see Table 1.

Table 1 - IR levodopa Equivalent Dose Conversion Factors

Previous medication	LD Conversion factor
LD+Opicapone	×1.4
LD+Entacapone	×1.33
LD+Tolcapone	×1.5
Stalevo	×1.33
Benserazide Methyldopa: Aldomet, Aldoril, Dopamet, Dopegyt DL-x-Difluoromethyl DOPA (DFMD) 3',4',5,7-Tetrahydroxy-8-methoxyisoflavone	×1
Controlled-release (CR) or Extended release (ER) Levodopa (e.g. Rytary, Numient)	×0.7

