6.5.2. Concomitant Therapy or Medication

Medications with start date or stop date on or after the first date of study drug dosing or ongoing at study completion will be considered concomitant medications.

Separate summaries of concomitant PD treatment medications (medications which start with ATC code N04) will be presented in tabular form using the ATC Level 4 and preferred term. Other concomitant medications will be presented in tabular form using the ATC Level 1, ATC Level 2, and Preferred Term (PT). Frequencies and percentages of patients receiving medications will be presented by treatment group and overall. The tables will be sorted by overall descending frequency of ATC Level(s) and then, within an ATC Level, by overall descending frequency of PT.

If the medication start date is incomplete, then it will be imputed as follows for the purpose of determining concomitant use:

- If the start date is completely missing, the start date will be equal to the first dose date. However, if the stop date is not missing and is before the first dose date, then the stop date will be used instead.
- If the start day is missing, the first day of the month will be used.
- If the start day and month are missing, then the first day of the first month (January) will be used.

If the medication stop date is partial, then it will be imputed as follows for the purpose of determining concomitant use:

- If the stop date is completely missing and the medication is not ongoing, the stop date will be equal to the last dose date or date of completion/withdrawal, whichever is the latest.
- If the stop day is missing, the last day of the month will be used.
- If the stop day and month are missing, then the last day of the last month (December) will be used.

The summary of prior and concomitant medications will be done for the Safety set broken down by treatment group.

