8.2. Exploratory Efficacy Variable(s) and Analysis

8.2.1. Change in daily “ON” time without troublesome dyskinesia (“GOOD ON”) from Baseline to each visit

The changes from baseline to all post-baseline visits within each treatment regimen and the difference between the 2 treatment regimens in “GOOD ON” time (defined as the sum of "ON" time without dyskinesia and “ON” time with non-troublesome dyskinesia) will be estimated using a Mixed Model for Repeated Measures (MMRM). The model includes response data from all post-baseline visits with no imputation for missing data. The “GOOD ON” time at baseline will be included as a covariate and the treatment regimen (Regimen 1 or Regimen 3), visit (Month 1, 3, 6, 9 or 12) and the interaction between treatment regimen and visit will be included as fixed factors in the model. An unstructured covariance structure will be assumed and the denominator degrees of freedom will be computed using the Kenward-Roger method. In case the model will not converge

with the unstructured covariance structure, the heterogeneous compound symmetry (CSH) and the heterogeneous Toeplitz structure (TOEPH) will be used instead (in that order). Both the changes from baseline within each treatment regimen and the difference between the regimens will be estimated, separately for each visit, from the same MMRM using contrasts. Since ON/OFF diaries were assessed differently for Cohort 1, this cohort will be excluded from the model.

The changes in “GOOD ON” time will be estimated both as hours (normalized to 16 hours of awake time) and as a percentage out of awake time during the 24 hours of data collection. However, only one p-value will be provided due to the fact that the p-values will be identical.

The SAS code planned for the analysis is outlined below.

```
PROC MIXED DATA=DATA;  
CLASS TRTP AVISIT USUBJID;  
MODEL CHG=BASE TRTP AVISIT TRTP*AVISIT / SOLUTION DDFM=KR;  
REPEATED AVISIT / SUBJECT=USUBJID TYPE=UN;  
LSMEANS TRTP*AVISIT / PDIFF CL;  
WHERE AVISIT IN ('MONTH 1', 'MONTH 3', 'MONTH 6', 'MONTH 9', 'MONTH 12' ) AND COHORT=2;  
RUN;
```

8.2.2. Change in daily “OFF” time based on home "ON/OFF" diaries from Baseline to the 12-month visit

The daily “OFF” time will be analyzed similarly as the “GOOD ON” time replacing baseline “GOOD ON” time with baseline “OFF” time as covariate.

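### The protocol's oral LD/DDI dose endpoint has no entry in SAP 4.0; secondarily, SAP treatment compliance is measured against a fixed full-regimen dose

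*Protocol*

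**What the plan says.** Protocol 7.3 sets the objective: "To assess the efficacy of continuous SC infusion of 2 dosing regimens of ND0612 on total daily dose of oral LD/DDI". Protocol 11.1.4.3.1 makes it the third of 15 exploratory endpoints: "Change in total daily dose of oral LD/DDI from Baseline to the 12-month visit". Protocol 11.1.4.3.2 gives a default (summary statistics by visit, and an MMRM for continuous endpoints) and then hands over the detail: "The definition of the endpoints and the statistical analyses will be detailed in the SAP".

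SAP 2.3 opens with "Exploratory efficacy objectives will be to assess the following" and gives eight bullets, none on oral levodopa dose. SAP 3.2.3 numbers 16 endpoints. Its dose items (3.2.3.5, 3.2.3.6 and 3.2.3.16) all concern ND0612. SAP 8.2.1 to 8.2.13 contain no oral dose analysis.

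Oral levodopa appears elsewhere in the SAP in three ways:
- SAP 6.3 summarises total daily levodopa dose, both unconverted and IR-equivalent (Table 1), as a baseline characteristic. SAP 4.5 uses a baseline cut at 400 mg for a subgroup.
- SAP 6.5.2 covers concomitant PD drugs by user counts: "Frequencies and percentages of patients receiving medications will be presented by treatment group and overall".
- SAP 5.1 provides listings: "All data from all patients entered into the study will be included in patient data listings".

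On compliance, SAP 7.4.2 divides the administered ND0612 levodopa by treatment days times 720 mg (Regimens 1 and 3) or 537.6 mg (Regimen 2). Protocol 8.4.9.3 sets no limit on the number of dose reductions.

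**The concern.** Protocol 6.5 says the study will explore whether additional oral anti-PD treatment is needed. Protocol 8.1.1 expects oral LD/DDI to be titrated down after the infusion starts and lets subjects take more as needed. In an open-label study with no control arm, a change in ON or OFF time is hard to read without the oral levodopa change over the same months. A programmer who works through the SAP's own endpoint list would not produce that output. Anyone who adds it later would have to choose the derivation after seeing data.

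The compliance ratio raises a smaller matter. A percentage labelled compliance should fall when a subject fails to take what was prescribed. With a fixed denominator it also falls when the investigator lowers the dose as the protocol allows.

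**Working it through.** **Cross-check of the 15 endpoints in Protocol 11.1.4.3.1 against SAP 3.2.3**
- Full entry (13): ON time without troublesome dyskinesia (3.2.3.1), OFF time (3.2.3.2), ND0612 dose change (3.2.3.5), ND0612 dose reducers (3.2.3.6), OFF responders (3.2.3.7), ON time with troublesome dyskinesia (3.2.3.8), PDQ-39 (3.2.3.9), EQ-5D-5L (3.2.3.10), UPDRS II (3.2.3.11), CGI (3.2.3.12), SGI (3.2.3.13), PDSS (3.2.3.14), UPDRS III (3.2.3.15).
- Half entry (1): the first 3 hours awake after 06:00. The protocol asks for percentage OFF and percentage Good ON; SAP 3.2.3.4 and 8.2.13 cover OFF only.
- No entry (1): oral LD/DDI dose.

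13 + 1 + 1 = 15.

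**Why the derivation matters.** The documents give no follow-up oral doses, so these patients are assumed; the factors are from SAP Table 1 (levodopa with entacapone 1.33, controlled or extended release 0.7). Entacapone is a permitted rescue drug under Protocol 8.4.9.2.

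| Assumed patient | Unconverted | IR-equivalent |
|---|---|---|
| 600 mg IR to 500 mg IR plus entacapone | 500 - 600 = -100 mg | 500 × 1.33 - 600 = +65 mg |
| 800 mg ER to 500 mg IR | 500 - 800 = -300 mg | 500 - 800 × 0.7 = -60 mg |

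In the first patient the sign reverses.

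**Compliance denominator.** The SAP's figures reproduce as rate × hours × 60 mg/mL:
- Regimen 1: (0.08 × 6 + 0.64 × 18) × 60 = 12.00 × 60 = 720 mg
- Regimen 2: 0.64 × 14 × 60 = 8.96 × 60 = 537.6 mg
- Regimen 3: 0.75 × 16 × 60 = 12.00 × 60 = 720 mg

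One 0.05 mL/h step is 0.05 × 18 × 60 = 54 mg/day in Regimen 1 and 0.05 × 16 × 60 = 48 mg/day in Regimen 3, consistent with the protocol's figure of about 50 mg. For a subject who takes exactly the reduced dose, three steps down on a fraction f of days, the score is 1 - f × 3 × step / 720:

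| f (assumed) | Regimen 1 | Regimen 3 |
|---|---|---|
| 0.25 | 94.4% | 95.0% |
| 0.50 | 88.8% | 90.0% |
| 1.00 | 77.5% | 80.0% |

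**Switchers.** Of 12 Regimen 2 subjects, 12 - 2 = 10 moved to Regimen 1, which is 10/210 = 4.8% of the protocol's planned number, or 10/170 to 10/120 = 5.9% to 8.3% of the range in SAP 3.3. SAP 7.4.2 does not say how their days are divided. If 720 mg were used throughout, a fully adherent switcher with an assumed m of 12 months on Regimen 2 would score (m × 537.6 + (12 - m) × 720) / (12 × 720), that is 97.9%, 93.7% or 87.3% for m = 1, 3 or 6. With days split at the switch the score is 100%.

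**The case against.** The strongest reply is that silence in the SAP does not remove the endpoint. SAP section 1 calls the SAP a complement to the protocol that prevails only where the two differ. Protocol 11.1.4.3.2 gives continuous endpoints a default analysis, and SAP 8.1 repeats the summary rule. SAP 6.3 already defines levodopa dose in two forms at baseline. This largely stands. A reader might infer that oral dose will go unanalysed, or that the study cannot answer its question about oral treatment; the documents do not support either reading. What remains is that the SAP's own endpoint list omits the endpoint, and neither document defines the post-baseline daily dose.

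The versions also differ. SAP 4.0 was written for protocol V9.0 and the protocol supplied is V10.0. A reader might infer that SAP section 10, which declares no changes from V9.0, is false. V9.0 is not available, so only a mismatch with the current protocol is established.

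On compliance, the output is descriptive, has no cut-off and defines no analysis set. SAP 7.2 separately reports how many subjects reduced ND0612 and by how much, and SAP 7.4.2 itself tabulates prolonged interruptions. Because SAP 7.4.2 gives Regimen 2 its own 537.6 mg, using 720 mg throughout for switchers is the less natural reading, so the switcher percentages show only what happens if no split is made. These points limit the harm but do not separate non-adherence from prescribed reduction.

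**Conclusion.** The omission is clear: one of 15 protocol endpoints has no SAP entry and a second has half of one. Its consequence is moderate, because a default method exists and the endpoint is exploratory. The conversion examples rest on assumed patients and show that the choice can change the sign, not how often it would.

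The compliance point also holds and is smaller. Three permitted steps held throughout put a fully adherent subject at 77.5% or 80.0%. The documents give no titration frequencies, so the effect on group means is unknown.

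A reader might extend either point to the main safety results. That is not supported: the adverse event, pain and tolerability analyses use neither variable.

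**What to change.** **Oral dose.** Add the objective to SAP 2.3 and the endpoint to 3.2.3 and 8.2. Derive the daily dose at each visit from the eCRF medication records and report it both unconverted and IR-equivalent, using the Table 1 factors. As the endpoint is a total, count the Regimen 3 morning dose and recorded as-needed doses, and name the days used; the two diary days before the visit would align it with ON/OFF time. For Cohort 2, use the 8.2.1 MMRM with baseline oral dose as covariate. Report Cohort 1 separately from its study 006 baseline (SAP 5.2 and 8.1). The statement in 8.2.1 that "this cohort will be excluded from the model" is there because of the diary, so it is no reason to leave Cohort 1 out here. Descriptive summaries suffice, since study 006 was to treat only 36 subjects.

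**First 3 hours.** Add percentage Good ON to SAP 3.2.3.4 and 8.2.13. Then check SAP section 10 against protocol V10.0.

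**Compliance.** If the administered dose is recorded independently of the pump setting, use the programmed daily dose by period as the denominator, split at each titration and at the Regimen 2 to 1 switch. If not, keep the present ratio and call it relative dose intensity.

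**Cost.** SAP wording and programming. Protocol 8.4.9 puts drug, dose and date on the eCRF, and 9.2.3 adds changes in oral LD/DDI. The CRF was not supplied, so capture of brief as-needed doses, and of administered dose apart from the pump setting, are assumptions to confirm. Vial accountability (Protocol 8.4.10) is independent of the pump setting, but a vial count does not give the volume infused.
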